2.3.3 Patients evaluable for DLT assessment (Phase 1 only)

The DLT evaluable population is defined as patients in the Phase 1 part receiving the planned doses of isatuximab and cemiplimab during Cycle 1, and who completed the DLT observation period of Cycle 1 after the first IMP administration, unless they discontinue the study treatment(s) due to DLT. Dose-limiting toxicity will be validated by the Study Committee. Patients not evaluable for DLT will be replaced.

2.3.4 Pharmacokinetic population

The PK population will be defined independently for isatuximab and cemiplimab, and includes patients from the all treated population with at least one reportable concentration after the study drug administration (whatever the cycle and even if dosing is incomplete).

2.3.5 ADA evaluable population

The ADA evaluable population will be defined independently for isatuximab and cemiplimab, and includes subjects with at least one sample, taken post-baseline after drug administration during the treatment or follow-up observation period, that is appropriate for ADA testing with a reportable result (positive, negative or inconclusive).

2.3.6 Biomarker population

There will be no population flag for biomarker. Biomarker endpoints will be analyzed using patients from the all treated population who have one assessment on the biomarker of interest unless otherwise specified.

2.4 STATISTICAL METHODS

Unless otherwise specified, analyses will be descriptive and performed separately for Phase 1 and Phase 2 patients, based on the analysis population defined in [Section 2.3](#).

For Phase 1 part, when the number of treated patient is small (<5), baseline information together with listings on response and adverse events will be provided. Summary tables might be presented if deemed appropriate.

In Phase 2 summary tables (except for demographics and baseline characteristics), treatment arms will be presented as follows:

- Isatuximab 10 mg/kg QW/Q2W (Isa).
- Isatuximab 10 mg/kg QW/Q2W + cemiplimab 250 mg Q2W (Isa + CemQ2W).
- Isatuximab 10 mg/kg QW/Q2W + cemiplimab 250 mg Q4W (Isa + CemQ4W).

Parameters on demographics and baseline characteristics would be provided by treatment arms and overall.

Continuous data will be summarized using the number of available data, mean, standard deviation (SD), median, minimum, and maximum for each arm. Categorical and ordinal data will be summarized using the number and percentage of patients in each arm.

2.4.1 Demographics and baseline characteristics

Parameters described in [Section 2.1.1](#) will be summarized using descriptive statistics on the AT/safety population in Phase 1 or ITT/randomized population in Phase 2. For Phase 2, analyses for the AT/safety population will be included in the appendices if the size of the randomized population is different (>10%) from the size of the all treated/safety population for any arm.

Past medical or surgical history will be summarized by primary SOC and PT (SOC will be sorted according to the internationally agreed order and PT by decreasing frequency) for randomized population in Phase 2.

2.4.2 Prior or concomitant medications (other than anticancer therapies)

The prior and concomitant medications will be presented for the AT/safety population in Phase 1 and the randomized population in Phase 2.

Medications will be summarized by arm and overall according to the WHO-DD dictionary, considering the first digit of the anatomic category class (ATC) (anatomic category) and the first 3 digits of the ATC class (therapeutic category). All ATC codes corresponding to a medication will be summarized, and patients will be counted once in each ATC category (anatomic or therapeutic) linked to the medication. Therefore, patients may be counted several times for the same medication.

The tables for prior, concomitant and post treatment medications will be sorted by decreasing frequency of ATC followed by all other therapeutic classes based on the incidence in the Isa + CemQ2W column. In case of equal frequency regarding ATCs (anatomic or therapeutic categories), alphabetical order will be used.

IR medications

Number (%) of patients with IR medications (including prophylaxis and curative intent) as defined in [Section 2.1.2](#) will be provided. Number (%) of patients with prophylactic IR medications including acetaminophen, diphenhydramine (or equivalent) and steroids will be provided by infusions. A similar summary will be provided for IR medications of curative intent.

2.4.3 Extent of investigational medicinal product exposure and compliance

The extent of study treatment exposure will be assessed and summarized on the AT/safety populations.

2.4.3.1 Overall exposure

The dose information will be assessed by the following variables to summarize the overall study treatment exposure (all study treatments together):

- Number of cycles started, defined by maximum of isatuximab/cemiplimab cycles started.
- Duration of overall exposure (or time on-treatment) (in weeks) is defined as (last day of last cycle - first day of first cycle)/7. The first day of first cycle is defined by the earliest of isatuximab and cemiplimab administration date. The last day of last cycle is defined by the last date among the following:
 - Date of last dose of isatuximab + 7 days if last cycle is QW cycle, or date of last dose of isatuximab + 14 days if last cycle is Q2W cycle,
 - Date of last dose of cemiplimab + 14 days if last cycle is Q2W cycle or date of last dose of cemiplimab + 28 days if last cycle is Q4W cycle (if applicable).

Total number of cycles started, number of cycles started by patients as a quantitative variable and by category (ie, number (%) of patients receiving at least 1 cycle, at least 2 cycles etc), duration of overall exposure will be summarized by descriptive statistics.

Cycle delay is defined as follows:

- A cycle is deemed as delayed if the start date of the current cycle - 28 - start date of the previous cycle is >3 days. Cycle delay is not defined for the first cycle.

Cycle delayed will be analyzed at the patient and cycle levels, as follows:

- Patient level:
 - Number of patients treated (used for % calculation in this section),
 - Number (%) of patients with a least 1 cycle delayed:
 - Number (%) of patients with a cycle delayed between 4 and 7 days (using maximum delay),
 - Number (%) of patients with a cycle delayed >7 days (using maximum delay).
- Cycle level:
 - Number of cycles (used for % calculation in this section),
 - Number (%) of cycles delayed:
 - Number (%) of cycles delayed between 4 and 7 days,
 - Number (%) of cycles delayed >7 days.

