13.4.2 Extent of investigational medicinal product exposure

The following variables will be described to summarize the overall study treatment exposure (all study treatments together):

- Overall number of cycles started.
- Overall duration of exposure in weeks defined as [(Last day of last cycle – first day of first cycle)/7].

The last day of last cycle is defined as the last date among the following:

- Date of last dose of isatuximab + 7 days if last cycle is QW cycle or date of last dose of isatuximab + 14 days if last cycle is Q2W,
- Date of last dose of cemiplimab + 14 days if last cycle is Q2W cycle or date of last dose of cemiplimab + 28 days if last cycle is Q4W cycle (if applicable).

The first day of first cycle is defined as the date patient receive first isatuximab or/and cemiplimab.

In addition, the following variables will be summarized with descriptive statistics for each IMP (ie, isatuximab and cemiplimab):

- Number of cycles started with each drug.
- Duration of exposure of each drug in weeks, defined as.
 - For isatuximab: [date of last dose of isatuximab + 7 days - first dose of isatuximab] /7 if last cycle is QW cycle or [date of last dose of isatuximab + 14 days - first dose of isatuximab]/7 if last cycle is Q2W cycle,
 - For cemiplimab: [date of last dose of cemiplimab + 14 days - first dose of isatuximab]/7 if last cycle is Q2W cycle or [date of last dose of isatuximab + 28 days - first dose of isatuximab]/7 if last cycle is Q4W cycle.
- Number of infusions.
- Cumulative dose (in mg/kg) for isatuximab/cemiplimab: The cumulative dose at is the sum of all doses administered from first to last dose.
- Actual dose intensity (ADI): defined as the cumulative dose divided by the duration of exposure.
- Relative dose intensity (RDI): defined as the ratio of the actual dose intensity to the planned dose intensity. The RDI is an indicator of the feasibility of the chosen schedule of administration.
- Cycle delays: A cycle is deemed to have been delayed if the start date is >3 days beyond the scheduled Day 1.

- Isatuximab infusion delays within a cycle: a dose is deemed to have been delayed if the study treatment is ≥ 2 days beyond the theoretical day of treatment for weekly dose, and ≥ 3 days beyond the theoretical day of treatment for Q2W schedule of administration. Infusion delay is not applicable to the 1st dose of each cycle.

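### The cycle-level delay percentages count every Cycle 1 in the denominator, although Cycle 1 cannot be delayed, so they understate the delay rate by a fraction that depends on treatment length

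*SAP*

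**What the plan says.** SAP 2.4.3.1 (Overall exposure) defines the event by the gap between consecutive cycle starts: "A cycle is deemed as delayed if the start date of the current cycle - 28 - start date of the previous cycle is >3 days". It adds that "Cycle delay is not defined for the first cycle". Delays are then tabulated at two levels, each with its own denominator:

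- patient level: "Number of patients treated (used for % calculation in this section");
- cycle level: "Number of cycles (used for % calculation in this section").

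The cycle-level denominator serves the overall row and also the two rows that split delays into 4 to 7 days and more than 7 days.

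The only definition of a cycle count in that section is "Number of cycles started, defined by maximum of isatuximab/cemiplimab cycles started", which includes Cycle 1. The section also plans the total number of cycles started and the "number (%) of patients receiving at least 1 cycle, at least 2 cycles etc". The population is set in SAP 2.4.3: "The extent of study treatment exposure will be assessed and summarized on the AT/safety populations".

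Protocol 13.4.2 gives the matching event rule, "A cycle is deemed to have been delayed if the start date is >3 days beyond the scheduled Day 1", but no denominator.

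**The concern.** A percentage of delayed cycles is naturally read as the chance that a cycle which could start late did start late. Here the denominator also holds cycles for which lateness has no meaning, one for each treated patient. The share of such cycles is fixed by how long patients stay on treatment, so the printed figure mixes delay with treatment length.

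The table will be read across three arms. Cycle delay is permitted in case of toxicity (Protocol 6.5.1), so readers will use it as a rough guide to how well each regimen could be kept on schedule. If patients in one arm stop sooner, that arm's cycle-level rate is diluted by a larger fraction. Two arms with the same delay rate among eligible cycles would then print different rates, with the shorter-treated arm looking better.

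**Working it through.** **Figure to reproduce.** None. Neither document states a delay percentage or an expected number of cycles, so the check is algebraic and illustrated over assumed ranges.

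**Inputs from the SAP.** Delay is undefined for Cycle 1; the cycle-level denominator is all cycles; the patient-level denominator is all treated patients (all from 2.4.3.1).

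**Assumed inputs.** Mean cycles per patient k from 2 to 12; at-risk delay rate p from 10% to 30%.

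**Cycle level.** Let N be treated patients and C cycles started, so k = C/N. Each treated patient has exactly one Cycle 1, so C - N cycles can be delayed. Expected delayed cycles = p(C - N).

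- Printed rate = p(C - N)/C = p(k - 1)/k
- Relative understatement = 1/k
- Absolute understatement = p/k

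| k | factor (k-1)/k | p = 10% prints | p = 20% prints | p = 30% prints |
|---|---|---|---|---|
| 2 | 0.500 | 5.0% | 10.0% | 15.0% |
| 3 | 0.667 | 6.7% | 13.3% | 20.0% |
| 4 | 0.750 | 7.5% | 15.0% | 22.5% |
| 6 | 0.833 | 8.3% | 16.7% | 25.0% |
| 8 | 0.875 | 8.8% | 17.5% | 26.3% |
| 10 | 0.900 | 9.0% | 18.0% | 27.0% |
| 12 | 0.917 | 9.2% | 18.3% | 27.5% |

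Two arms both at p = 20%:

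- k = 4 against k = 8: 15.0% against 17.5%, an artificial gap of 2.5 points.
- k = 4 against k = 10: 15.0% against 18.0%, an artificial gap of 3 points.

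With C - N as denominator, every entry in a column returns to its p.

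**Relative or absolute.** The relative loss 1/k is always larger where k is smaller. The absolute loss p/k need not be: at k = 4 and p = 10% it is 2.5 points, while at k = 8 and p = 30% it is 3.75 points.

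**Patient level, for comparison.** If q of N patients start only Cycle 1, the planned percentage is (N - q)/N times the percentage among patients with at least 2 cycles. With the planned 35 per arm and an assumed 10 patients delayed, the plan prints 10/35 = 28.6%. Among patients with at least 2 cycles the figure is 28.6% at q = 0, 10/33 = 30.3% at q = 2, 10/30 = 33.3% at q = 5 and 10/28 = 35.7% at q = 7.

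Changing this denominator would not remove the dependence on treatment length. Assume geometric cycle counts with mean m and a 20% chance of delay in each cycle after the first. The probability of no delay is (1/m) / [1 - 0.8(1 - 1/m)].

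- m = 4: 0.25/0.40 = 0.625, so 37.5% of treated patients have a delay. Among the 75% with at least 2 cycles it is 37.5/0.75 = 50.0%.
- m = 8: 0.125/0.30 = 0.417, so 58.3% of treated patients. Among the 87.5% with at least 2 cycles it is 58.3/0.875 = 66.7%.

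The gap between arms falls only from 20.8 to 16.7 points, so about 80% of it remains (16.7/20.8).

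**The case against.** The strongest reply is that little is lost. The table is descriptive, carries no test and triggers no decision. The same section plans the total cycles started and the number of patients treated, so a reader can subtract one from the other and recover the right denominator. Events that led to a dose delay are tabulated separately by drug (SAP Table 7), and relative dose intensity is reported for each drug (SAP 2.4.3.2 and 2.4.3.3). All of this stands and keeps the point minor. It does not justify printing a percentage that the reader has to correct.

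It can also be said that the cycle count might be meant to leave out Cycle 1. The SAP does not say so, and its only definition of the count includes Cycle 1. The general rule in SAP 2.5.3 on non-missing denominators is written for patients, not cycles, so it does not settle the matter.

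A reader might infer that the patient-level percentage is wrong in the same way. The documents do not support that. The percentage of treated patients with at least one delayed cycle is a well-defined quantity, and all treated patients is the SAP's convention for patient-level delay, omission and interruption in 2.4.3.2 and 2.4.3.3. A denominator of patients who reached Cycle 2 would condition on what happens after randomisation and drop those who stopped after Cycle 1, possibly for toxicity. As the working shows, it would also leave most of the dependence on treatment length in place.

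**Conclusion.** The point holds at cycle level. On the plain text, the printed percentage is the at-risk rate times (k-1)/k, and whenever any delay occurs it lies below that rate. The direction needs no assumption; the size does. At an assumed 20% the table would show 15.0% with 4 cycles per patient and 18.0% with 10.

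Three broader readings should be resisted:

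- That every delay percentage in every arm is wrong. At patient level the choice of denominator makes no difference in an arm where nobody stops after Cycle 1; elsewhere the planned figure answers a different, valid question.
- That the shortest-treated arm always suffers most. This is exact for the relative understatement at cycle level. The absolute gap can reverse when delay rates differ, and at patient level the driver is the share of patients with a single cycle.
- That the safety objective is compromised. Protocol 9.1 bases the safety profile on examinations, laboratory tests and adverse events; cycle delay is a supporting exposure summary.

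The impact is minor.

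**What to change.** In SAP 2.4.3.1, at cycle level, replace the denominator with the number of cycles started from Cycle 2 onward (total cycles started minus treated patients), and apply it to the overall row and to both duration rows. Keep the definition of delay unchanged.

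Keep all treated patients as the patient-level denominator. A percentage among patients who started at least 2 cycles may be shown beside it, labelled as such.

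The cost is one line of SAP wording and one changed denominator in one table. No new data are needed, and no dose or treatment rule is touched. The cycle-level delay rates will read slightly less favourably.

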2.4.3.2 Isatuximab exposure

The isatuximab dose information will be assessed by the following:

- Total number of cycles started.
- Number of cycles started by patient.

- Duration of isatuximab exposure (or time on-treatment) (in weeks) is defined depending on the isatuximab administration schedule as follows:
 - If drug is discontinued at a cycle with QW isatuximab administration: [date of last dose of isatuximab + 7 days - date of first dose of isatuximab]/7,
 - If drug is discontinued at a cycle with Q2W isatuximab administration: [date of last dose of isatuximab + 14 days - date of first dose of isatuximab]/7.
- Actual dose (mg/kg): for a given cycle and day of administration, the actual dose in mg/kg corresponds to the actual dose in mg administered at each time point divided by the actual body weight as measured at each time point (cycle and day).
- Cumulative dose (mg/kg): the cumulative dose is the sum of all actual doses of isatuximab, expressed in mg/kg, given from first to last administration.
- Actual dose intensity (ADI) in mg/kg/week: defined as the cumulative dose (in mg/kg) divided by the duration of isatuximab exposure (in weeks).
- Relative dose intensity (RDI) in %:

$$100 \times \frac{\text{ADI (mg/kg/week)}}{\text{Planned Dose Intensity (mg/kg/week)}}$$

Planned dose intensities in mg/kg/week corresponds to the planned dose (10 mg/kg) multiplied by the theoretical total number of doses during the started cycles (count 2 for Q2W cycles, 4 for QW cycles), and divided by the theoretical cycle duration expressed in weeks (ie, 4 weeks per cycle started).

The total number of cycles started, number of cycles started by patients as a quantitative variable and by category (ie, number [%] of patients receiving at least 1 cycle, at least 2 cycles, etc), duration of isatuximab exposure, cumulative dose, ADI and RDI will be summarized by descriptive statistics.

The following variables will be derived to describe dose delays/modifications:

- Dose delay (within a cycle): A dose is deemed as delayed if the actual start date of the infusion - theoretical start date of an infusion is >1 day for weekly administration, is >2 days for Q2W administration. Dose delay does not apply to the first infusion of each cycle.
- Infusion interruption: An infusion will be considered to be interrupted (as collected on CRF) if the isatuximab administration is stopped during an infusion before it is completed regardless of whether it is further restarted or not.
- Dose omission: a dose is considered omitted if the dose is not administered for the scheduled visit and there are positive dose(s) afterwards.

Dose delayed/modification will be analyzed at the patient, cycle and the total number of isatuximab administration levels as follows:

- Patient level (number of all treated patients will be used for % calculation):
 - Number (%) of patients with at least 1 dose delay,
 - Number (%) of patients with at least 1 dose omission,
 - Number (%) of patients with a least 1 infusion interrupted:
 - Number (%) of patients with a least 1 infusion interrupted and re-started,
 - Number (%) of patients with a least 1 infusion interrupted and not re-started,
 - Number (%) of patients with at least 2 infusions interrupted.
- Infusion level
 - Total number of infusions (used for % calculation for this section),
 - Number (%) of infusions interrupted:
 - Number (%) of infusions interrupted and re-started,
 - Number (%) of infusions interrupted and not re-started,
 - Number (%) of infusions interrupted more than once,
 - Number of infusion interrupted at (with % calculated using the total number of infusions interrupted): 1st infusion, 2nd infusion, subsequent infusions,
 - Time from infusion start to first interruption in minutes (quantitative and qualitative: 5-10, 11-30, 31-60, 61-90, 91-120, >120).

Duration of isatuximab infusion (in hours) is defined as the time from the start (date/time) of isatuximab infusion to the end (date/time) of isatuximab infusion in the same visit. It will be summarized for first and subsequent infusions.

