- Bone Marrow for disease assessment ^{ee}	X	to confirm CR and as clinically indicated						X (if clinically indicated)	X (if clinically indicated) ^{dd}		
- Bone disease assessment (Skeletal survey or low-dose whole body CT) ^{ff}	X					X (if clinically indicated)		X (if clinically indicated)	X (if clinically indicated) ^{dd}		
- Plasmacytoma assessment (PET/CT/MRI) ^{gg}	X					X (if clinically indicated)		X (if clinically indicated)	X (if clinically indicated) ^{dd}		
Isatuximab Administration ^{hh}		X	X	X	X	X	X				

Evaluation ^a	Screening/ Baseline	Cycle 1 ^b				Subsequent Cycles ^b		End of Treatment (EOT)	Post treatment Follow-up Period ⁱⁱ		
	D-21 to D1	D1	D8	D15	D22	D1	D15	30 days after last IMP admin	At 60 days after last IMP admin	At 90 days after last IMP admin	Beyond 90 days after last IMP admin
Cemiplimab Administration		X		X		X	X				
AE/SAE Assessment ⁱⁱ	X	Continuously throughout study period						X (ongoing related AE, ongoing SAE, new related AE/SAEs)			
Prior/Concomitant Medication	X (within 21 days prior to first dose)	Continuously throughout study period						X (related to AE/SAEs)			
- New anticancer therapy								X	X		

- a **Evaluation:** Assessments to be performed prior to study treatment and prior to premedication administration unless otherwise indicated. Informed consent should be signed before any study specific procedures. In Phase 2 part, **randomization** to take place once the consented patient has completed all the necessary screening procedures and is deemed eligible for study entry by the Investigator or designee. All eligible patients must be randomized using Interactive Response Technology (IRT). Every effort should be made to start treatment within 3 working days of randomization.
- b **Cycle:** A cycle is 28 days. The treatment window is ± 1 day for each of the weekly administrations ± 2 day for each of the Q2W administrations and ± 4 day for each of the Q4W administrations. A dose is deemed to have been delayed if the treatment is ≥ 2 days beyond the theoretical day of treatment for weekly dose, ≥ 3 days beyond the theoretical day of treatment for Q2W dose and ≥ 5 days beyond the theoretical day of treatment for Q4W dose. The reason for dose delay will be captured. Cycle 1 Day 1 refers to the day the patient receives the first study treatment administration.

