8.3 DOSING REGIMEN AND SEQUENCE

8.3.1 Dosing regimen

Isatuximab:

- For isatuximab alone as control, and at DL1 and DL-1: 10 mg/kg QW for 4 weeks followed by Q2W (ie, on Days 1, 8, 15 and 22 in Cycle 1, and on Days 1 and 15 in Cycle 2 and beyond, of a 28-day cycle).
- For DL-2: 10 mg/kg Q2W (ie, on Days 1 and 15 every cycle, of a 28-day cycle).

Cemiplimab:

- For DL1: 250 mg Q2W (ie, on Days 1 and 15 in all cycles of a 28-day cycle).
- For DL-1 and DL-2: 250 mg Q4W (ie, on Day 1 in all cycles of a 28-day cycle).

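### Isatuximab relative dose intensity divides actual and planned dose by different lengths of time, so on-schedule dosing reads above 100% when the last dose is Day 1 of Cycle 2 or later

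*SAP*

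**What the plan says.** SAP 2.4.3.2 builds isatuximab RDI as actual dose intensity over planned dose intensity, times 100.

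- **Actual dose intensity** is "defined as the cumulative dose (in mg/kg) divided by the duration of isatuximab exposure (in weeks"). Duration is "date of last dose of isatuximab + 14 days - date of first dose of isatuximab]/7" when the drug is stopped in a Q2W cycle, and "date of last dose of isatuximab + 7 days - date of first dose of isatuximab]/7" when it is stopped in a QW cycle.
- **Planned dose intensity** starts from 10 mg/kg per infusion ("Planned dose intensities in mg/kg/week corresponds to the planned dose (10 mg/kg")). This is multiplied by the doses foreseen in all started cycles (4 for a QW cycle, 2 for a Q2W cycle), "and divided by the theoretical cycle duration expressed in weeks (ie, 4 weeks per cycle started").

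Protocol 8.3.1 puts the infusions "on Days 1, 8, 15 and 22 in Cycle 1, and on Days 1 and 15 in Cycle 2 and beyond", and the Protocol 1.1 footnotes state "A cycle is 28 days". Protocol 13.4.2 uses the same exposure-duration rule, does not define planned intensity, and says "The RDI is an indicator of the feasibility of the chosen schedule of administration".

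**The concern.** The numerator of the ratio ends two weeks after the last dose. The denominator runs to the end of the last started cycle. When the last dose is Day 1 of a Q2W cycle, the denominator is two weeks longer and includes one further infusion.

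Those two extra weeks carry 10 mg/kg, or 5 mg/kg/week. That is below the average planned rate, because Cycle 1 runs at 10 mg/kg/week. Including them in the plan but not in the actual figure lowers only the denominator, so the ratio rises.

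Stopping after a Day 1 dose is an ordinary event. Under the Protocol 1.1 footnotes, response is assessed from samples taken on Day 1 before dosing, and the cycle may start before results are available. A patient can therefore be dosed on Day 1 and stop before Day 15. At stake is whether the isatuximab RDI table can be read at face value for early stoppers.

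**Working it through.** The documents state no isatuximab RDI value, so there is no figure to reproduce. The check applies the SAP formulas to the nominal schedule.

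**Inputs.** 10 mg/kg per infusion; 4 infusions in Cycle 1 and 2 in each later cycle; 28-day cycles; tail of 7 days (QW) or 14 days (Q2W).

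**Last dose on Day 1 of Cycle k, k ≥ 2**

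- Doses given: 4 + 2(k − 2) + 1 = 2k + 1
- Duration: 4(k − 1) + 2 = 4k − 2 weeks
- Actual intensity: 10(2k + 1)/(4k − 2)
- Planned doses: 4 + 2(k − 1) = 2k + 2, over 4k weeks; planned intensity: 10(2k + 2)/(4k)
- RDI = k(2k + 1)/[(2k − 1)(k + 1)]

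| Last dose | Given | Actual (mg/kg/week) | Planned (mg/kg/week) | RDI |
|---|---|---|---|---|
| Cycle 2 Day 1 | 5 | 50/6 = 8.33 | 60/8 = 7.50 | 111.1% |
| Cycle 3 Day 1 | 7 | 70/10 = 7.00 | 80/12 = 6.67 | 105.0% |
| Cycle 4 Day 1 | 9 | 90/14 = 6.43 | 100/16 = 6.25 | 102.9% |
| Cycle 5 Day 1 | 11 | 110/18 = 6.11 | 120/20 = 6.00 | 101.9% |
| Cycle 6 Day 1 | 13 | 130/22 = 5.91 | 140/24 = 5.83 | 101.3% |

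**Where the formula behaves.** A stop after Day 15 of Cycle k gives 2k + 2 doses over 4k weeks, which equals the plan: 100%. A stop in Cycle 1 after n doses gives 10n/n = 10 against 40/4 = 10: 100%.

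**Effect on omissions.** With one earlier dose omitted and a last dose on Cycle 2 Day 1, the SAP gives (40/6)/7.5 = 88.9%. On a matched interval it is 4 of 5 scheduled doses, 80.0%. If the same patient also receives Cycle 2 Day 15, the SAP gives 5/6 = 83.3%, which is correct.

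**Effect on delays.** For a Cycle 2 Day 1 stop, RDI stays at or above 100% until total delay exceeds (50/7.5 − 6) × 7 = 4.7 days. A 4-day cycle delay, which SAP 2.4.3.1 counts as delayed (more than 3 days), gives a duration of 46/7 = 6.57 weeks and RDI = (50/6.57)/7.5 = 101.4%. On the matched interval it is 6/6.57 = 91.3%.

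**Comparison with cemiplimab.** SAP 2.4.3.3 uses a constant planned rate. For a Q2W patient stopping at Cycle 2 Day 1, (750/6)/125 = 100%. The same patient at the same visit reads 111.1% for isatuximab.

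**The case against.** The strongest reply is that this is a choice of convention in a descriptive table. If the Day 15 dose of the last started cycle counts as planned, the Cycle 2 Day 1 stopper should read 5/6 = 83.3%; if it does not, 100%. That choice is open in principle, but the SAP makes neither: its mixed formula returns 111.1%, which neither consistent interval gives. The truncated interval has the better claim, because it follows the exposure-duration rule in Protocol 13.4.2 and agrees with the cemiplimab formula.

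The limits on scope also stand. Only last doses on Day 1 of a Q2W cycle are affected, the excess fades quickly, and all three Phase 2 arms share the isatuximab schedule, so the formula itself favours no arm.

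A reader might infer three stronger things that the documents do not support:

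- **That missed doses are hidden.** An earlier omission still lowers RDI, to 88.9% in the worked case, and is counted in the omission summary. Only doses left ungiven at the end of treatment escape: the omission rule in SAP 2.4.3.2 requires a later dose. The truncated interval does not reveal these either.
- **That early toxicity would pass for over-dosing.** SAP 2.2 reports reasons for discontinuation and SAP 2.4.5.2 reports adverse events leading to it. Protocol 10.5 defines overdose per infusion, not through RDI.
- **That feasibility of the combination is judged on RDI.** Protocol 13.4.2 calls it one indicator of schedule feasibility. Phase 1 addresses feasibility through the dose-limiting toxicity rule in Protocol 6.2.1.

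**Conclusion.** The isatuximab RDI formula is wrong as written for one class of patients: those whose last dose is Day 1 of Cycle 2 or later. With on-schedule dosing the excess is 11.1 percentage points at Cycle 2, 5.0 at Cycle 3, 2.9 at Cycle 4 and about 1 by Cycle 6.

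These figures assume full 10 mg/kg doses on nominal days. They are not an absolute ceiling: giving Cycle 2 Day 1 two days early, within the visit window, yields (50/5.71)/7.5 = 116.7%. How far a summary mean or median moves depends on how many patients stop at such visits, which the documents do not give.

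RDI is only summarised descriptively. The response-rate test, the futility rule and dose selection do not use it. This is a minor correction.

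**What to change.** In SAP 2.4.3.2, define planned intensity on the interval that actual intensity uses:

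planned intensity = 10 mg/kg × doses scheduled through the visit of the last dose ÷ scheduled weeks from Cycle 1 Day 1 to that visit, plus 7 days (QW) or 14 days (Q2W).

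For a Cycle 2 Day 1 stop this is 50/6 = 8.33 mg/kg/week, so on-schedule dosing reads 100%.

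Add one line to the exposure table: the number of patients with isatuximab doses left ungiven in their last started cycle. Neither the corrected RDI nor the omission count shows these.

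The cost is one formula and one table row, from dosing dates already collected. If the exposure tables have been produced, rerun the isatuximab RDI summary or footnote the mismatch.
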